Official title: A Randomized Trial Examining Plasma Exchange using the BD Catheter In an Outpatient Apheresis Unit (REPLACE)

NCT number: NCT04253756 IRB Approved date: 4/22/2020 A Randomized Trial Examining Plasma Exchange using the BD Catheter In an Outpatient AphCresis Unit (REPLACE)

PI: [name] [name], CMSRN, QIA

Faculty Sponsor: [name] MD

Co-Investigator: [name], RN

Research manager: [name] PhD

Date: 11/27/2019

Version: 1

Introduction and Purpose

Nurses and apheresis technicians caring for patients requiring therapeutic apheresis procedures (TAP) utilize a wide range of intravenous catheters to obtain the access required to perform their procedures(Kalantari, 2012), (Golestaneh & Mokrzycki, 2013). The standard of care for our facility is to use an 18-gauge apheresis needle (Medisystems®) for the access site and an 18-gauge autogard catheter for the return site. Unfortunately, there is minimal literature defining best practices for catheter size selection(Salazar et al., 2017). At UT Southwestern Medical Center, our goal is to provide peripheral therapy to reduce the need for central access, such as a medical ports or tunneled catheters(Spires et al., 2018). However, the requirement for an 18 gauge catheter for an adequate return site, at times, rules out the patient for peripheral therapy(Putensen, Leverett, Patel, & Rivera, 2017). This requires central venous access to be obtained, which can delay the start of the procedure.

The lack of scientific evidence to support the use of smaller peripheral return catheters has increased the use of implanted ports in our institution(Putensen et al., 2017). The objectives of our pilot study are patient-centered and include analyzing the safety of using smaller peripheral return catheters without increasing the risk of hemolysis.

Background and Significance

TAP treats a wide range of disease processes and, in all cases, requires inlet and return venous access to perform the procedure. The goal of TAP is to return the patient to baseline and maintain independence and function. A larger needle (18 gauge) can cause more discomfort to the patient as well as additional scarring. A smaller needle may present less discomfort and scarring to the patient. Our goal in our outpatient clinic is to minimize disruption to the patient's routine and help them maintain normal activities of daily living.

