To accomplish these goals, our outpatient clinic is open Monday thru Friday offering 4 different appointment times. All patients that are referred to our clinic for TAP, first receive a vein evaluation to see if the patient is a candidate for peripheral IV therapy. At our clinic, approximately 68% of our TAP's are performed peripherally. This eliminates the risk of a central line infection and any alteration in activities of daily living, such as bathing(Kramer, 2016), (Shang, Ma, Poghosyan, Dowding, & Stone, 2014),(Keller et al., 2018; McDiarmid, 2015).

Our hypothesis, is that the 20-gauge BD Nexiva Diffusics catheter provides the same efficacy as current practice with no increase in adverse events for patients undergoing therapeutic apheresis. The results from our study will be significant because if the 20 guage needle is equally effective for TAP, it can increase the number of patients that would be candidates for peripheral therapy. Therefore, decreasing the need for central venous access, which place the patient at an increased risk of infection. Our study is a comparison of 2 types of infusion catheters. The standard of care is an 18-gauge autogard catheter (control group) which will be compared to the 20-gauge BD Nexiva Diffusics (intervention).

- P patients who require therapeutic apheresis procedures (TAP)
- I use of 20G BD diffusics catheter during apheresis
- C use of 18 G standard of care IV catheter during apheresis
- O no difference in efficacy and no increase in safety events

Concise Summary of Project

This is a randomized pilot study of TAP using the current standard of care catheter (SOC) vs the BD Nexiva Diffusics Catheter. It is a single blinded, randomized study. Data will be used to refine and power a full randomized control trial. For this study, a sample of 33 encounters in each group (total of 66 encounters). Our specific aim is to test the hypothesis that the 20-gauge BD Nexiva Diffusics Catheter provides the same efficacy and lower pain level with no increase in adverse events for patients undergoing apheresis treatments.

Randomization Procedure

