After an eligible participant is consented to the study the patient will be randomized without replacement to the use of one of the two catheters. Using a random number generator, numbers between (1-66) were randomly divided into two groups: SOC Control group and BD Intervention group (Figure 1). A study identification number (SID) key will be saved on a UTSW approved secure device and only the research coordinator will have access to the SID key showing which SID coordinates with each group. This will ensure that unblinding can occur is necessary and there is a backup to randomization.

The research coordinator will have 66 randomized envelops without replacement. Half of the envelops will be assigned to 18G catheter SOC (control) and the other half be assigned to

20G BD Nexiva Diffusics catheter (intervention). The PI will be blinded, therefore the PI will pick an envelope when patients are consented and ready for treatment. Participants will be randomized after they have consented to the study. Participants' will then be randomized to one of the two groups again at each encounter (i.e., SOC visit). Inside the envelope it will tell the investigator if the patient is in the control or intervention group of the study.

To promote a more representative sample, each patient may participate a maximum of 10 times.

Study procedure:

[figure not shown]
Each enrolled patient will participate in the study will be randomized at each encounter. During each encounter the following information will be captured:

- 1. CBC
- 2. Patient discomfort

level with placement of catheter

- 3. Inlet rate
- 4. Return line pressures
- 5. Procedures alarms
- 6. Procedure total time
- 7. Post procedure sample

Treating nurse (RN) will start the TAPs procedure with one of the 2 catheters. During the intervention period, the RN will be at bedside during as it is SOC in the Apheresis unit however for the purpose of this study the RN will have the study data collection form (DCF, Appendix1). The RN will complete the pre-assessment including a pain assessment to establish pain level prior to procedure that is currently documented in the electronic medical record. The patient will be asked to self-report the pain level after the return line has been started on the visual analog scale (VAS) Scale from 0mm to 100mm "0 being the lowest/ no pain, 100mm being the highest

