Instructions:	Please complete the following form except for the VAS scale. Must be completed by patient to measure the characteristics of pain severity. Please circle option that apply.					
Collect CBC	Yes	Νο				
Catheter type	18 GA BD Autogard	20 GA BD Nexiva Diffusics				
Vein diameter w/tourniquet:	Vein diameter w/o turniquet:	Vein diameter Procedure Running:				
Asses pain after return placement						
Please rate your current pain by drawing a vertical line across the bar below						

vere		Extremely Severe		
		Procedure d	ata	
tart time:				
Inlet rate	Return line pressures	Alarms	Comments	
	tart time:	tart time: Inlet rate Return line	Procedure da tart time: Inlet rate Return Alarms line	

Total Procedure time:	Procedure en	Procedure end time:		Final Inlet Volume/Blood Processed:	
Collect post proceduer Plasma Hemoglobin	Yes		No		

References

- Golestaneh, L., & Mokrzycki, M. H. (2013). Vascular access in therapeutic apheresis: update 2013. *Journal of clinical apheresis, 28*(1), 64-72.
- Kalantari, K. (2012). The choice of vascular access for therapeutic apheresis. *Journal of clinical apheresis*, 27(3), 153-159.
- Keller, S. C., Williams, D., Rock, C., Deol, S., Trexler, P., & Cosgrove, S. E. (2018). A new frontier: Central line–associated bloodstream infection surveillance in home infusion therapy. *American journal of infection control*, 46(12), 1419-1421.
- Kramer, N. (2016). Monitoring Central Line-Associated Bloodstream Infections (CLABSI) in Home Infusion. *Infusion*, 22(4), 35-44.
- McDiarmid, S. (2015). Reduce the risk of infection by reducing the need for central lines: using ultrasound guidance to establish peripheral access in patients with sickle cell disease undergoing red cell exchange apheresis. *Journal of clinical apheresis*, *30*(2), 98-99.

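### The protocol does not require the return vein to be identified and recorded before the envelope is opened, so a nurse who knows the gauge could choose the vein by arm.

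*Combined protocol and SAP*

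**What the plan says.** - **Allocation.** Under Randomization Procedure, "the PI will pick an envelope when patients are consented and ready for treatment", and "Inside the envelope it will tell the investigator if the patient is in the control or intervention group of the study". Allocation is repeated at each encounter, up to 10 times per patient.
- **Who knows the gauge.** Under Study procedure, "Treating nurse (RN) will start the TAPs procedure with one of the 2 catheters". Concise Summary of Project states that "It is a single blinded, randomized study", and the only role named as blinded is the PI.
- **Vein assessment.** Background and Significance says that referred patients "first receive a vein evaluation to see if the patient is a candidate for peripheral IV therapy". This concerns candidacy and is not described as fixing the return vein for a given encounter. Appendix 1 has fields for vein diameter at the encounter, the first being "Vein diameter w/tourniquet", then without tourniquet and with the procedure running. It has no field for which vein or site was used, or for a vein named before allocation.
- **Analysis.** The Statistical Analysis Plan compares plasma hemoglobin and minutes to complete the procedure by group, using ANOVA, and names no vein covariate. Return pressure appears only in a secondary analysis against the share of the lumen occupied. Lower pain is in the specific aim, and Study procedure says VAS is collected to compare the groups, but the Statistical Analysis Plan names no analysis for it.

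**The concern.** Randomising an encounter balances what is fixed before the envelope is opened. It does not balance a choice made afterwards by someone who knows the arm. The protocol itself treats gauge as bearing on which veins are usable: Introduction and Purpose says that "the requirement for an 18 gauge catheter for an adequate return site, at times, rules out the patient for peripheral therapy". With a new allocation at each visit, the vein can also be chosen afresh each time.

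Two outcomes are exposed. Procedure time is one of the two efficacy measures, and Potential Risks supplies a route to it: an inadequate return triggers alarms, repeated alarms lead to a lower inlet rate, and a slower inlet can lengthen the procedure. VAS pain is scored once the return line has been started, and puncture site may plausibly affect it.

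If the vein did differ by arm, more encounters would not remove the distortion, and it would carry into the full trial that this pilot is meant to inform. Nor would adjustment for a diameter measured after allocation repair it, because that diameter may itself depend on the arm.

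**Working it through.** **Reading the sections together**

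1. Randomization Procedure sets the time of the envelope only by the patient's readiness. It says nothing about the vein.
2. Study procedure has the nurse start with the allocated catheter, so the nurse knows the gauge when placing it.
3. No section says when, or by what rule, the return vein is chosen for an encounter.
4. Appendix 1 collects diameters but not the vein, the site or the time of measurement relative to the envelope. The completed form could not show whether vein choice followed the arm.

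The plan gives no figure on this point to reproduce. It also states no alpha, power, effect size or SD behind its 33 encounters per group. What follows is illustrative, and every input other than 33 is assumed.

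**Context for 33 per group** (two-sided alpha 0.05 assumed, clustering of repeat encounters ignored)

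- Standard error of the difference in SD units: √(2/33) = 0.246.
- Detectable difference at 80% power: (1.960 + 0.842) × 0.246 = 0.69 SD. At 90% power: (1.960 + 1.282) × 0.246 = 0.80 SD.

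**Effect of arm-dependent vein choice on a continuous outcome**

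Let a share f of 20G encounters use a different vein from the one an 18G would have used, and let that change the outcome by s SD. The bias is b = f × s. With no true catheter effect, the chance of a significant result is Φ(b/0.246 − 1.96) + Φ(−b/0.246 − 1.96).

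- f = 10%, s = 0.25: b = 0.025 SD, 5.1%.
- f = 25%, s = 0.5: b = 0.125 SD, 8.0%.
- f = 50%, s = 0.5: b = 0.25 SD, 17.4%.
- f = 50%, s = 1: b = 0.50 SD, 52.8%.

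**The same reasoning on the VAS scale**

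Bias in mm = shift in the share of punctures at a more painful site × pain difference between sites. With assumed shifts of 10 to 40 percentage points and differences of 10 to 20 mm, this runs from 0.10 × 10 = 1 mm to 0.40 × 20 = 8 mm.

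The range spans trivial to serious, and nothing in the documents places the trial within it.

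**The case against.** **The order of steps is not stated.** A reader might infer that the envelope is opened before the vein is chosen. The documents do not say so. A patient described as ready may already have a vein picked out, and a figure under Study procedure is not available in the text reviewed. The form does not settle it: catheter type is listed above the vein diameters, but the diameter taken while the procedure is running is listed above the pain rating and the start time, so the rows are not chronological. The two tourniquet diameters may well be measured before cannulation. This objection stands. What remains is that nothing requires the vein to be named first.

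**A different vein may be part of the intervention.** The protocol values the 20G because it could make more patients candidates for peripheral therapy. If the question is the 20G as used in practice, a vein chosen to suit it belongs to the effect and is not bias. Against that, Background and Significance describes the study as comparing two kinds of infusion catheter, which favours a device question. The protocol does not settle which it means. For the same reason the documents do not support a rule that the same vein be used in either arm. Such a rule would answer only one of the two questions and would touch clinical practice.

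**The outcomes are not equally exposed.** A reader might infer a biased between-arm comparison of return pressure. The Statistical Analysis Plan contains none: pressure is related to lumen occupancy, where variation in vein size is part of the exposure. Pain has no named analysis, so the concern there applies to the comparison the specific aim implies. Procedure time is the clearest case.

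**Direction.** It is tempting to assume that a smaller catheter draws the nurse to a smaller or more distal vein. Nothing in the documents establishes that.

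**Conclusion.** The point holds as an omission. The nurse placing the catheter knows the gauge, and the protocol neither requires nor records a choice of return vein before the envelope is opened. Vein choice could therefore differ by arm in procedure time and in VAS pain, and the data as planned could not show whether it had.

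Bias is possible, not demonstrated. The figures of 1 to 8 mm and 5.1% to 52.8% rest on assumed frequencies and effects of vein change, and the percentages also assume a two-sided 5% test on independent encounters. Whether a difference in vein would count as bias at all depends on whether the protocol intends a comparison of catheters or of strategies. This is an inexpensive improvement to a pilot, not a defect that undermines the design.

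**What to change.** 1. In Randomization Procedure, add that before the envelope is opened the nurse identifies the intended return vein by current practice, and records its site and its with- and without-tourniquet diameters.
2. In Appendix 1, place these fields above catheter type. Add the vein actually used and the reason for any change.
3. Report departures from the intended vein by arm.
4. In the Statistical Analysis Plan, use the pre-envelope diameter as a baseline covariate in the comparison of procedure time by arm, and in the comparison of pain once that analysis is specified. The covariate improves precision and corrects chance imbalance. It does not undo a change of vein made after allocation, which is why the departures must be reported.
5. State whether the comparison is of the two catheters in the same intended vein or of the 20G strategy as used. The recording in steps 1 to 3 serves either.

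The cost is a protocol sentence, a few new form fields (site, vein used, reason for change) and a reordered bedside step. The diameters are already collected, and the nurse's choice of vein is not constrained.

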Measures of Quality of Apheresis will include inlet rate, and return pressures, procedure time. These measures are all readily available in the electronic medical record (EMR) and are all currently recorded as standard of care. The inlet rate is defined as the percent of patient inlet rate divided by the maximum allowable inlet rate. Because inlet rates are different for each type of TAP has a different maximum inlet rate, this will allow standardization across procedures. The max inlet rate for Photopheresis is 50ml/sec, the max inlet for plasma exchange is 100ml/sec inlet for red blood cell exchange is 55ml/sec. In addition, the inlet rate for each participant in the intervention arm will be compared to the average of their last 5 procedures. This measure will compare the efficiency of the SOC verses the intervention.

Inclusion Criteria

- Adult (≥ 18 years old)
- Speaks and reads English
- A patient of the Apheresis clinic at UT Southwestern University Hospital and Clinics
- Scheduled to receive TAP (therapeutic plasma exchange, red blood cell exchange and extracorporeal Photopheresis) as standard of care

Exclusion Criteria

- Prisoners
- Persons under the age of 18 years
- Patient who are actively involved in chemotherapy

Sources of Research Material

There are three sources of data for this study: electronic medical record (EMR) and paper-and-pen data collection from the patient's bedside (Data Collection form), and lab results provided by the UTSW laboratory via EMR. The EMR data that will be collected will include demographic information such as: age, sex, race, ethnicity, and admission diagnosis. The paper-and pen-data collection will include the patient self-reported pain level (VAS Scale), CBC collection, procedure data (minutes, inlet rate, return line pressures and alarms) total procedure time and post procedure sample. The paper-and-pen data collection form (Appendix 1) will record data only during patients TAP's encounter. Blood sample will be obtained from a SOC line. An additional 8 ml's for blood will be drawn from the patients for research purposes. Results from the bloodwork will be provided by the UTSW laboratory via the patient's EMR.

Recruitment Methods and Consenting Process

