be replaced with the SOC 18-gauge catheter. Obtaining blood samples may cause some discomfort, feeling lightheaded, fainting, bruising, clotting, and bleeding from the site of the needle stick and, in rare cases, infection. The risks are mitigated by drawing blood from a line that has already been established as part of SOC.

There is a low risk of breach in confidentiality. Subjects will be assigned individual study identification (SID) numbers and no personal identifiers will be included in the final summary.

Patients who are randomized to the 20-guage needle group and who fail the intervention will be given the 18-guage standard of care needle. At the patient's next visit, the patient will once again be randomized. If the patient is randomized into the 20-guage needle arm and fails the intervention a second time, the patient will be removed from the study.

Procedures to Maintain Confidentiality

Study participants will be given a study identification (SID) number. Only the approved study personnel and the principal investigator have access to the database linking the SID to the patient name. This database is kept on a protected drive on a password protected computer. Paper or hard copy participant records will be kept in a locked file cabinet in a locked office. If any identifying information is transmitted, it will be done so via secure e-mail and/or dedicated fax machines.

Statistical Analysis Plan

All data will be first collected on the DCF (Appendix I) and then entered into an electronic spreadsheet (e.g., MS Excel) which will be converted to SAS v 9.4 for analysis. All statistical analyses will be performed at UTSW in a location with secure data encryption capability. Initially, the data will be summarized first using standard measures of central tendency (mean, median, standard deviation, and interquartile range) for each variable. These will be examined to support the assumption of being approximately normally distributed. Baseline characteristics will be summarized using appropriate parametric and non-parametric measures.

The primary hypothesis is that the 20-gauge BD Nexiva Diffusics catheter provides the same efficacy of current practice with no increase in adverse events for patients undergoing therapeutic apheresis. This will be examined in 2 steps. First, ANOVA will be used to explore

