efficacy wherein efficacy is represented by 1) the plasma hemoglobin value, and 2) the amount of time (minutes) required to complete a TAP. Hence models will be constructed to compare the mean plasma hemoglobin values by group, and to compare the mean number of minutes to complete TAP by group. Second, ANOVA will be used to compare the mean number of adverse events subjects experience in each group (intervention vs control).

Finally, a planned secondary analysis is to examine if the percent of lumen occupied by the return catheter is associated with return pressures. The suggested standard is that a catheter occupies < 45% of the inner-lumen diameter (measured with ultrasound). Return pressures >400 mm Hg are considered problematic. Chi-square analysis will be used to explore the odds of experiencing a return pressure > 400 mm Hg when the return catheter occupies <45% of the inner-lumen diameter.

Item	Month 1-2	Month 3-6	Month 4-8	Month 9-11	Month 12-18
IRB approval	Х				
Consent/	Х	X			
Enrollment					
Randomization	Х	X	Х	Х	
Data collection	Х	Х	Х	Х	
Manuscript				Х	X
prep					
Study closeout					X

Project Timeline

Enrollment of first patient (month 1), enrollment of the last patient (month 12), completion of data analysis (month 14), and manuscript submission (month 18). The apheresis team see approximatley 3000 TAP treaments each year. Of these, approximately 1500 encounters will meet the primary inclusion criteria. We anticipate that it will take less than 1-year to complete the study.

Future directions

The intention of this pilot study is to test the 20-gauge BD Nexiva Diffusics Catheter performance and efficacy. The findings from this study will be used to provide additional preliminary data to BD to support a National Institutes of Health or Agency for Healthcare Research and Quality (AHRQ) application (pending 2017 AHRQ funding announcements). Stakeholder feedback will be provided through an optional de-identified report to all patients and families.

Presentation of data

It is anticipated that the results from this study will be presented to American Society for Apheresis at their annual convention. The results will also be summarized in a manuscript and submitted for peer-review publication to Journal of Clinical Apheresis.

Appendix 1

Patient Sticker

A Randomized Trial Examining Plasma Exchange using the BD Catheter In an Outpatient Apheresis Unit The "REPLACE" study

Date SID Procedure Type						

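### Adverse events are part of the primary hypothesis but are neither defined nor given a data item, so events other than hemolysis, alarms and pain would reach the analysis only through incidental notes

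*Combined protocol and SAP*

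**What the plan says.** The Statistical Analysis Plan states as the primary hypothesis that the 20-gauge catheter "provides the same efficacy of current practice with no increase in adverse events for patients undergoing therapeutic apheresis". Efficacy is examined first, through plasma hemoglobin and procedure minutes. For the second step, "ANOVA will be used to compare the mean number of adverse events subjects experience in each group (intervention vs control").

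Four places describe what is collected.

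- Study procedure: "During each encounter the following information will be captured", followed by CBC, discomfort at placement, inlet rate, return line pressures, alarms, total time and a post-procedure sample. Later text in that section adds that hemolysis is scored present or absent at each encounter.
- Sources of Research Material: "There are three sources of data for this study", namely the electronic record, the bedside form and the laboratory. For the first, "The EMR data that will be collected will include demographic information such as: age, sex, race, ethnicity, and admission diagnosis". The bedside form is said to hold pain, CBC, procedure data, time and sample, and to cover the encounter only.
- Statistical Analysis Plan: "All data will be first collected on the DCF (Appendix I") and then moved to a spreadsheet.
- Appendix 1: the visible fields are CBC, catheter type, vein diameters, pain scale, inlet rate, return pressures, alarms, Comments, times, volume processed and plasma hemoglobin.

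Potential Risks lists "discomfort, feeling lightheaded, fainting, bruising, clotting, and bleeding from the site of the needle stick", and rarely infection, but as consequences of blood sampling. It also describes replacement of a failing 20-gauge catheter by the 18-gauge one.

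**The concern.** A comparison of event counts needs a count for every encounter, including a recorded zero. Without a definition, a prompt or a field, a blank cannot be told apart from an encounter with no event, and analysts cannot reconstruct the difference afterwards.

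The direction matters. The hoped-for result is no increase. Missed events pull both arms toward zero and so toward that result. The treating nurse starts the procedure with the assigned catheter and completes a form on which the catheter type is circled, so whether something is noted can depend on the arm. Uneven noting would bias the difference in a direction that nobody could check.

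The trial is a pilot meant to refine and power a full trial. Event rates taken from unprompted notes are a poor basis for that.

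**Working it through.** This is a question of data capture. The plan's only design figure, 33 × 2 = 66 encounters, is consistent but has no stated event rate, power or margin behind it, so no figure of the plan's own can be reproduced on this point. The check sets the sections side by side.

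1. **Needed:** a number of adverse events per encounter, by arm (Statistical Analysis Plan).
2. **Definition:** no section gives a definition, a list of expected catheter-related events, a recorder or an observation window.
3. **Captured items (Study procedure):** 0 of 7 are adverse events.
4. **Data sources (Sources of Research Material):** adverse events are not named in the described contents of any of the 3.
5. **Form (Appendix 1):** no adverse-event field is visible. Comments is the only visible free-text column in the procedure table. Catheter failure or replacement has no visible field either.
6. **Safety-related data that are collected:** plasma hemoglobin after every encounter, alarms every 15 minutes, and pain on a 100 mm scale. None is designated an adverse event. Plasma hemoglobin is an efficacy measure in the Statistical Analysis Plan, and alarms are given no analysis role.
7. **Later events:** the form covers the encounter only, so bruising or infection that appears afterwards has no planned route into the data.

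The arithmetic below gives context only. It treats encounters as independent, which is optimistic because one patient may contribute up to 10.

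- **Upper bound with 0 events in 33:** 1 − 0.05^(1/33) = 0.087, one-sided 95%. The upper limit of a two-sided 95% interval is 1 − 0.025^(1/33) = 0.106.
- **Chance that an arm shows any event:** 1 − (1 − p)^33. If half of events are missed (assumption), a true rate of 10% is seen as 5% and the chance falls from 97% to 82%. A true rate of 2% is seen as 1% and the chance falls from 49% to 28%.
- **Power of a two-sided exact Fisher test at 0.05, 33 per arm, by enumeration.** This is not the planned test, and all rates are assumptions:

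| True rates | Full capture | Half captured |
|---|---|---|
| 30% vs 5% | 70% | 21% (15% vs 2.5%) |
| 10% vs 5% | 2.5% | 0.2% (5% vs 2.5%) |

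In the first row the capture loss is decisive. In the second the sample size is already the limit.

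**The case against.** The strongest reply is that safety is measured. Hemolysis is the one risk named in the Introduction's objectives, and it is laboratory-tested at every encounter. Alarms and pain are also recorded in both arms. This stands, and it rules out the reading that the trial has no systematic safety data. It does not close the gap, because the plan does not count any of these as adverse events and the planned count has no other source.

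A reader might also infer, from the statement that all data pass first through the form, that an event can enter only if the nurse writes it under Comments. The documents do not support that. Study procedure sends laboratory results directly to the PI and into a spreadsheet, and the electronic record is a separate source whose list is open-ended. The chart could hold an event, but incidental charting is not systematic ascertainment.

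The figure under Study procedure is not shown and the form's table is broken in extraction, so an item visible only there cannot be excluded. The prose description of the form under Sources of Research Material makes that unlikely.

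Finally, the 70% to 21% fall in power could be taken as the size of the problem. It rests on one unsourced pair of rates. At 10% vs 5%, power is 2.5% even with complete capture.

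**Conclusion.** The concern holds in a limited form. Adverse events are a component of the primary hypothesis with a planned between-arm comparison, yet they are undefined and have no item in the captured list, the described sources or the visible form. The plan leaves open whether hemolysis, alarms and catheter failure count. Other events would be recorded incidentally, largely by staff who know the catheter, so a finding of no increase would be weak evidence and possibly biased.

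The size of the bias cannot be stated, because the documents give no event rate and no capture rate. The structural finding (0 of 7 items, no named source content, no visible field) needs no assumption beyond the extraction limits noted above. The 8.7% bound assumes independent encounters and complete capture; it describes the sample size and is separate from the capture gap. The point should be corrected before enrolment but does not invalidate the pilot's other aims.

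**What to change.** **Appendix 1.** Add an adverse-event checklist with a yes/no answer and a count, completed for every encounter in both arms before the patient leaves. It should cover access-site and procedural events of the return catheter, with an entry for other events. The investigators should write the list for the catheter; the harms under Potential Risks are attributed to blood sampling, which both arms share, and do not serve as that list. Add one question at the next scheduled visit for later events such as bruising or infection, asked before the new envelope is opened and attributed to the arm of the earlier encounter.

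**Study procedure and Sources of Research Material.** Name adverse events as a captured item, with the recorder and the observation window.

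**Statistical Analysis Plan.** Define the outcome from the checklist. State whether hemolysis and alarms count as adverse events or as efficacy. Report 20-gauge failure or replacement separately: it is described for that arm only, so including it in a composite would build in an imbalance. Report the difference by randomised arm with a 95% confidence interval that allows for repeated encounters per patient. Any power figure should be labelled illustrative and given as a range.

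**Cost.** About a minute per encounter (estimate), by a nurse already at the bedside with the form. The nurse still knows the catheter, so prompting reduces uneven recording but does not remove it.
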